## Research Related Risks

If you uploaded a separate research protocol document in the 'Research Protocol' page, cite the applicable section and page numbers from that document in the answer box below.

- 1 \* Individually list each research-related risk, using a separate line for each. Next to each risk, delineate the likelihood/seriousness of the risk, and the provisions for minimizing the risk:

Salsalate:

1- Tinnitus. Somewhat likely and not serious. On a weekly basis, participants will undergo side effect checklist assessment of commonly occurring drug side effects, with a specific question included to address this side effect. If the participant is unable to tolerate the drug at the target dose of 4 grams per day then 500 mg reductions will be made in a stepwise fashion until the tinnitus remits or a minimum dose of 2 grams per day is reached.

2 - Headache. Not likely and not serious. On a weekly basis, participants will undergo side effect checklist assessment of commonly occurring drug side effects, with a specific question included to address this side effect.

3 - Dizziness. Not likely and not serious. On a weekly basis, participants will undergo side effect checklist assessment of commonly occurring drug side effects, with a specific question included to address this side effect.

4 - Nausea, dyspepsia, and the remote possibility of GI bleeding. Not likely and possibly serious. These are less common side effects and occur infrequently in individuals taking the drug for only 6 weeks. On a weekly basis, participants will undergo side effect checklist assessment of commonly occurring drug side effects, with specific questions included to address these side effects. If a participant develops GI bleeding the drug will be stopped immediately .

5 - Pregnancy risks. Somewhat likely and serious. There is some evidence with medications similar to Salsalate that an unborn child may have trouble with the heart forming correctly. If a woman is pregnant or planning on becoming pregnant she cannot participate in this study .

Fluvastatin:

1 - Headache. Somewhat likely and not serious. On a weekly basis, participants will undergo side effect checklist assessment of commonly occurring drug side effects, with a specific question included to address this side effect.

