7 - Hepatotoxicity. Not likely and possibly serious. This is a less common side effect and occurs infrequently; "Initial post-marketing surveillance studies of the statins revealed an elevation in hepatic transaminase to values greater than three times the upper limit of normal, with an incidence as great as 1%. The incidence appeared to be dose related. However, in the placebo-controlled outcome trials in which 10- to 40-mg doses of simvastatin, lovastatin, fluvastatin, atorvastatin, pravastatin, or rosuvastatin were used, the incidence of 3-fold elevations in hepatic transaminases was 1-3% in the active drug treatment groups and 1.1% in placebo patients (Law et al., 2006; Ridker et al., 2008). No cases of liver failure occurred in these trials. Although serious hepatotoxicity is rare, 30 cases of liver failure associated with statin use were reported to the FDA between 1987 and 2000, a rate of about one case per million person-years of use (Law et al., 2006)." (Burton et al. 2011). The FDA has recently concluded that serious liver injury with statins is rare and unpredictable in individual patients, and that routine periodic monitoring of liver enzymes does not appear to be effective in detecting or preventing this rare side effect. However, on a weekly basis, participants will undergo side effect checklist assessment of commonly occurring drug side effects. If participants exhibit signs or symptoms of hepatitis then laboratory tests evaluating liver function will be ordered and the medications will be stopped immediately .

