8 - Myopathy. Not likely possible serious. This is a less common side effect. "The major adverse effect associated with statin use is myopathy (Wilke et al., 2007). Between 1987 and 2001, the FDA recorded 42 deaths from rhabdomyolysis induced by statins. This is a rate of one death per million prescriptions (30-day supply). In the statin trials described earlier (under "Hepatotoxicity"), rhabdomyolysis occurred in eight active drug recipients versus five placebo subjects. Among active drug recipients, 0.17% had CK values exceeding 10 times the upper limit of normal; among placebo-treated subjects, the incidence was 0.13%. Only 13 out of 55 drug-treated subjects and 4 out of 43 placebo subjects with greater than 10-fold elevations of CK reported any muscle symptoms (Law et al., 2006). Concomitant use of drugs that diminish statin catabolism or interfere with hepatic uptake is associated with myopathy and rhabdomyolysis in 50-60% of all cases (Law and Rudnicka, 2006; Thompson et al., 2003). These medications including gemfibrozil (38%), cyclosporine (4%), digoxin (5%), warfarin (4%), macrolide antibiotics (3%), mibefradil (2%), and azole antifungals (1%) (Thompson et al., 2003) will be excluded." (Burton et al. 2011) On a weekly basis, participants will undergo side effect checklist assessment of commonly occurring drug side effects. If participants exhibit signs or symptoms of myopathy, then laboratory tests evaluating creatinine protein kinase (CPK; a marker of muscle breakdown) will be ordered. If CPK is not markedly elevated (i.e., 3x normal), then the medication will be continued and CPK will be monitored on a weekly basis. If CPK is elevated, then the medications will be stopped immediately .

9 - Pregnancy risks. Somewhat likely and serious. Fats circulating in the body are important for the proper development of an unborn child. Fluvastatin lowers the fats circulating in the blood and may adversely affect the normal development of an unborn child. Women who are pregnant or planning on becoming pregnant will not be able to participate in this study .

Omega-3-fatty acids:

1 - Dyspepsia. Somewhat likely and not serious. On a weekly basis, participants will undergo side effect checklist assessment of commonly occurring drug side effects.

2 - Eructation. Somewhat likely and not serious. On a weekly basis, participants will undergo side effect checklist assessment of commonly occurring drug side effects.

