### 3.1 If Yes, when?

## 4 \* Briefly describe the DSM review process itself. Will it be an open or closed review to the investigator? Blinded/unblinded data? How will confidentiality of individual participant data be maintained?

Data and Safety Monitoring Board. The MPRC has established a Data and Safety Monitoring Board (DSMB), which is comprised of two psychiatrists, a statistician, a pharmacist, and a community representative. The psychiatrists are experts in the clinical treatment of people with schizophrenia. None of the DSMB members reviewing this study will be investigators on the proposed project; however, [name] serves as a non-voting member of the DSMB to assist in the monitoring of all MPRC trials. The DSMB will be charged with the following responsibilities:

- 1) to establish a regular meeting schedule;
- 2) to review the proposed protocol;
- 3) to review the proposed consent form prior to IRB submission;
- 4) to monitor study progress and the occurrence of side effects/adverse events, and serious adverse events throughout the course of the study; and
- 5) to review with [name], the statistician for the project, the study data management system.

The DSMB will review reports on protocol progress, side effects and adverse events twice a year. In addition, all serious adverse events (SAEs) will be reported to the DSMB, P.I., the University of Maryland School of Medicine IRB, and the appropriate NIH program of ficer. The P.I. will receive all SAE reports within 24 hours of their occurrence. The DSMB, University of Maryland School of Medicine IRB, and NIH program officer will receive the reports within 48 hours. If the incidence of any side effect/adverse event is 25% or more or any SAE occurs in excess in either treatment group, then the DSMB will notify the P.I. The P.I. and DSMB will determine whether possible protocol modifications are required to minimize the further occurrence of such events.

SAEs will be defined as any adverse experience that is unexpected or: i) results in death; ii) results in persistent or significant disability/incapacity; iii) results in or prolongs an existing inpatient hospitalization (even if the hospitalization is a precautionary measure for observation); iv) is a congenital anomaly/birth defect in of fspring of subjects taking the product regardless of time to diagnosis; v) is cancer; vi) is the result of an overdose, whether accidental or intentional; or vii) is a suicide attempt (but not suicidal ideation).

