**Objective Criteria for Termination of Protocol:**

Any of the following conditions will result in protocol termination.

- a. The subject is judged to be entering a clinically significant exacerbation of his/her illness by their treating clinician.
- b. Either of the following:
  1. Relative to the baseline Brief Psychiatric Research Scale (BPRS) item scores, an increase of 3 points or more OR an increase from 5 to 7 on any one of the following BPRS items: somatic concern, conceptual disorganization, hostility, suspiciousness, hallucinatory behavior, or unusual thought content.
  2. An increase of 2 or more on the Clinical Global Impression – global severity rating.
- c. Complete cessation of eating and drinking for a period exceeding 24 hours.

Serious Adverse Events are reported immediately to the IRB, to the DHMH IRB, to the Inpatient Program/Chief, to the MPRC Head and to the SGHC Clinical Director. Where appropriate, a report is also sent to the FDA. A serious adverse event (SAE) is any adverse experience that:

- Results in death.
- Results in persistent or significant disability/incapacity.
- Results in or prolongs an existing inpatient hospitalization (even if the hospitalization is a precautionary measure for observation).
- Is a congenital anomaly/birth defect in offspring of subjects taking the product regardless of time to diagnosis.
- Is cancer.
- Is the result of an overdose, whether accidental or intentional.
- Is a suicide attempt (not suicidal ideation only)
- For outpatient participants: Is an admission to an inpatient facility.
- For inpatient participants:
  1. Is the participant being placed in locked door seclusion for a period exceeding 2 hours?
  2. Is the participant being placed in physical restraints?
  3. Is an elopement from the facility defined as an unauthorized absence exceeding 12 hours or documentation as elopement in the clinical chart?

ID: VIEW4E1B0261D940  
Name: v2\_Monitoring Plan - Internal DSM

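### Neither SAE list covers life-threatening or medically important events, so GI bleeding, liver injury or myopathy managed without admission has no assured place in expedited reporting

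*Combined protocol and SAP*

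**What the plan says.** Monitoring Plan - Internal DSMB defines a serious adverse event twice.

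Item 4, on the review process, begins "SAEs will be defined as any adverse experience that is unexpected or: i) results in death; ii) results in persistent or significant disability/incapacity". It continues "iii) results in or prolongs an existing inpatient hospitalization (even if the hospitalization is a precautionary measure for observation", then birth defect, and ends "v) is cancer; vi) is the result of an overdose, whether accidental or intentional; or vii) is a suicide attempt (but not suicidal ideation". The same text recurs in the second copy of the application. This list sits with the timed route (investigator within 24 hours; DSMB, IRB and NIH programme officer within 48 hours) and with the DSMB trigger. That trigger fires when any side effect or adverse event reaches 25% incidence, or when any SAE occurs in excess in either treatment group.

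Item 5, on termination criteria, starts afresh: "A serious adverse event (SAE) is any adverse experience that". It repeats the outcome limbs, drops *unexpected*, and adds "For outpatient participants: Is an admission to an inpatient facility" and, for inpatients, seclusion, restraint and elopement. Its route is immediate reporting to the IRBs and local heads. The DSMB is not among the recipients named there.

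Research Related Risks rates three harms as not likely but possibly serious and attaches an action to each:
- Salsalate item 4, GI bleeding: "If a participant develops GI bleeding the drug will be stopped immediately".
- Fluvastatin item 7, hepatotoxicity, on signs or symptoms of hepatitis: "laboratory tests evaluating liver function will be ordered and the medications will be stopped immediately".
- Fluvastatin item 8, myopathy, after CPK is measured for signs or symptoms: "If CPK is elevated, then the medications will be stopped immediately". If CPK is not markedly elevated, drug continues with weekly CPK.

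None of these three entries calls for an SAE report or any expedited report.

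**The concern.** An SAE definition decides which single events reach the investigator and the DSMB in days rather than months. Both lists here work by outcome, and neither has a limb for an event that is life-threatening or that is medically important in itself. The gap falls on organ toxicities for which the plan itself stops study drug.

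Two safeguards depend on the definition: the 24/48-hour reports and the DSMB's by-arm comparison of SAEs. If a bleed, a liver injury or a CPK-confirmed myopathy is managed as an outpatient, the text does not assure that either safeguard will see it. Merging the two lists as they stand would not help, because the two limbs are missing from both.

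**Working it through.** The plan gives no figure to reproduce. The check is mainly textual, with some arithmetic for scale.

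**1. The two lists side by side**

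| Limb | Item 4 | Item 5 |
|---|---|---|
| Unexpected, on its own | Yes, undefined | No |
| Death | Yes | Yes |
| Persistent or significant disability | Yes | Yes |
| Hospitalisation, including precautionary | Yes | Yes, plus any admission of an outpatient |
| Birth defect, cancer, overdose, suicide attempt | Yes | Yes |
| Seclusion, restraint, elopement (inpatients) | No | Yes |
| Life-threatening | No | No |
| Medically important | No | No |

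**2. The three harms, managed without admission and without persistent or significant disability**

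- Item 5: no limb applies, so the event is not an SAE.
- Item 4: only *unexpected* could apply. All three harms are named risks, so on the ordinary reading they are expected. A GI bleed can be argued either way, because the background (Justification, Objective, & Research Design, item 4) says salsalate is not associated with gastric bleeding.

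**3. What remains for an event that is not an SAE**

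- Periodic DSMB review. The interval is annual in Monitoring Plan - Committee (item 3) and in the annual-meeting paragraph, twice a year beside the SAE definition, and quarterly in a later paragraph of item 4.
- The 25% trigger. With 30 per arm (Study Procedures, item 1), 0.25 × 30 = 7.5, so 8 participants are needed. With 10 in an arm, 0.25 × 10 = 2.5, so 3 are needed.
- An interim summary precipitated by an event, and as-needed Closed Sessions (both in item 4). Neither has an event list or a deadline.

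**4. How often such events might arise, using rates the plan quotes for statins**

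The chance of at least one among 30 on active drug is 1 − (1 − p)^30.

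- Three-fold transaminase elevation, p = 0.01: 1 − 0.99^30 = 26%.
- The same, p = 0.03: 1 − 0.97^30 = 60%.
- CK above 10 times the upper limit, p = 0.0017: 1 − 0.9983^30 = 5%.

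At p = 0.03 the binomial chance of 8 or more in 30 is about 2 in a million. One or two cases are plausible, but reaching the 25% trigger in a full arm is not. These are laboratory rates; not every elevation would be symptomatic or be confirmed as injury. The quoted placebo rate of 1.1% alone gives 1 − 0.989^30 = 28%, so a single case need not be due to drug.

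**5. How many more could be randomised before the next review**

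Sixty participants over the planned three years (Study Procedures, item 4) is 60/36 = 1.67 per month.

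| Review interval | Further randomised, at most | On active drug |
|---|---|---|
| 12 months | 20 | 10 |
| 6 months | 10 | 5 |
| 3 months | 5 | 2 or 3 |

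An event falling at a random point in the interval gives half of these on average. If the three years must also contain one 16-week participation (about 3.7 months), accrual runs over 32.3 months at 1.86 per month, and the maxima become about 22, 11 and 6.

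**The case against.** Much of the case on the other side is sound and limits what can be claimed.

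- A reader might infer that these harms are never SAEs without admission, lasting disability or death. The text does not support that. The disability limb is met by persistent *or* significant incapacity, so a severe but temporary illness can qualify. Precautionary admission counts, and most life-threatening events would lead to admission. Item 4 also has the *unexpected* limb, undefined though it is.
- A reader might infer that a non-SAE reaches the DSMB only at its next scheduled review. The event-precipitated summary and the as-needed Closed Sessions, for which adverse events are named separately from SAEs, say otherwise. They are discretionary and undated, so they soften the gap without closing it.
- It is tempting to call these the toxicities the combination is most likely to cause. The plan rates each as not likely. Tinnitus, headache, dyspepsia and myalgia are among those rated somewhat likely.
- It is also tempting to set a reportable ward absence against unreported liver injury within the DSMB trigger. Elopement is only in item 5's list, whereas the trigger sits with item 4's list.
- Specified side effects are compared by arm with Fisher's exact test whatever their SAE status (Sample Size and Data Analysis, secondary outcomes). That is an end-of-study analysis and does nothing for timely reporting.
- A Full Study Protocol file is listed under Additional Documents and was not available. Its SAE definition could not be checked. However, the Research Protocol page says that there is no separate protocol to upload and that the application holds the study information.

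What stands is that both limbs are absent from both lists, and that the status of a named harm managed without admission rests on an undefined word in one list and is excluded in the other.

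**Conclusion.** The point holds as a gap in the reporting rule. For GI bleeding, hepatotoxicity or myopathy with raised CPK, managed without admission or persistent or significant disability, SAE status is excluded under item 5 and doubtful under item 4. Entry to the 24/48-hour route and to the excess-SAE trigger is therefore not assured.

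The consequence is delay rather than certain loss, because the events would still reach periodic review. The upper bounds of 20, 10 or 5 further randomisations assume even accrual and that no discretionary route is used. They measure exposure to an unreviewed signal and do not count people harmed. The conclusion should be corrected in the protocol, but it does not call the efficacy analysis into question.

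**What to change.** Reconcile items 4 and 5 of Monitoring Plan - Internal DSMB into one SAE definition that serves both reporting and the DSMB trigger. In it:

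- Settle whether *unexpected* stands alone, and define it if it is kept.
- Add a limb for an event that is life-threatening.
- Add a limb for a medically important event, expressly including GI bleeding, confirmed liver injury, and a CPK elevation for which the plan already stops study drug. The liver wording matters: the plan stops drug on signs or symptoms, before laboratory results, so tying SAE status to the stop alone would send unconfirmed symptoms down the expedited route. The sponsor should state what counts as confirmation.
- Send these events down the existing 24/48-hour route and count them in the by-arm SAE comparison.
- If the merged list keeps seclusion, restraint and elopement, tabulate them separately from medical SAEs.

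The cost is one wording amendment and some additional expedited reports, whose number the documents do not allow one to predict. No dose, stopping rule or study procedure changes.

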## 5 \*What are the criteria defined in the protocol to be used for decision making regarding continuation, modification, or termination of study?

**Symptom re-emergence.** The course of schizophrenia includes periods when symptoms become worse. This occurs in standard clinical treatment, and may continue to occur during research participation. Some research protocols may be associated with an increased risk of symptom re-emergence, for instance an experimental drug that turns out to be ineffective, or if the participant is in a drug-free or placebo period. Participants in drug studies are closely monitored for increased symptoms and side effects. When clinically necessary the protocol is interrupted and an individual is put back on non-experimental medication. We have also developed a procedure to assess worsening objectively (see below):

**Objective Criteria for Termination of Protocol:**

Any of the following conditions will result in protocol termination.

- a. The subject is judged to be entering a clinically significant exacerbation of his/her illness by their treating clinician.
- b. Either of the following:
  1. Relative to the baseline Brief Psychiatric Research Scale (BPRS) item scores, an increase of 3 points or more OR an increase from 5 to 7 on any one of the following BPRS items: somatic concern, conceptual disorganization, hostility, suspiciousness, hallucinatory behavior, or unusual thought content.
  2. An increase of 2 or more on the Clinical Global Impression – global severity rating.
- c. Complete cessation of eating and drinking for a period exceeding 24 hours.

Serious Adverse Events are reported immediately to the IRB, to the DHMH IRB, to the Inpatient Program/Chief, to the MPRC Head and to the SGHC Clinical Director. Where appropriate, a report is also sent to the FDA. A serious adverse event (SAE) is any adverse experience that:

- Results in death.
- Results in persistent or significant disability/incapacity.
- Results in or prolongs an existing inpatient hospitalization (even if the hospitalization is a precautionary measure for observation).
- Is a congenital anomaly/birth defect in offspring of subjects taking the product regardless of time to diagnosis.
- Is cancer.
- Is the result of an overdose, whether accidental or intentional.
- Is a suicide attempt (not suicidal ideation only)
- For outpatient participants: Is an admission to an inpatient facility.
- For inpatient participants:
  1. Is the participant being placed in locked door seclusion for a period exceeding 2 hours?
  2. Is the participant being placed in physical restraints?
  3. Is an elopement from the facility defined as an unauthorized absence exceeding 12 hours or documentation as elopement in the clinical chart?

ID: VIEW4E1B0261D940  
Name: v2\_Monitoring Plan - Internal DSM

## Research-Related Costs

### 1 \*Is the study's financial supporter (e.g., commercial sponsor, federal or state grant or contract, private foundation, physician-sponsor) covering any research-related costs?

Yes

- 1.1 If Yes, check all that apply:  
 Research-Related Services (personnel costs, tests, supplies, exams, x-rays, or consultations required in the study)  
 Investigational or Study Drug  
 Investigational Procedure(s)
- 1.2 If No, who is responsible for payment?
- 2 \* Who is responsible for the uncovered research-related costs?  
 There will be no uncovered research-related costs
- 2.1 If Other, specify:
- 3 If the participant is responsible for any research-related costs, identify and estimate the dollar amount:  
 None

ID: VIEW4E1B5D964180f  
 Name: v2\_Research Related Cost

